O.D. -2.50D / -1.25D x 180° 20/20
O.S. -2.00D / -1.00D x 180° 20/20

Choose a diagnostic lens for each eye with axis 180°. Place the lens on each eye and allow a minimum of 3 minutes for it to equilibrate, based on the patient's initial response to the lens. If the lens has not yet stabilized, recheck until stable.

Check the orientation of the axis mark. If the bottom axis mark is in the 6 o'clock position on both eyes, choose the appropriate cylinder as listed previously. If the lens has not yet stabilized, recheck until stable.

Here is the Rx Prescribed:

O.D. -2.50D / -1.25D x 180°
O.S. -2.00D / -0.75D x 180°

Example 2

Manifest (spectacle) refraction:

O.D. -3.00D / -1.00D x 90° 20/20

O.S. -4.75D / -2.00D x 90° 20/20

Choose diagnostic lenses of -3.00D / -0.75D x 90° for the right eye and -4.50D / -1.75D x 90° for the left eye, the nearest lenses available to the spherical power, cylinder power, and axis needed. For the left eye, since the manifest refraction called for -4.75D, compensating for vertex distance the sphere is reduced by 0.25D to -4.50D. The cylinder power will be -1.75D. Place the lens on each eye and allow a minimum of 3 minutes for it to equilibrate, based on the patient's initial response to the lens. If the lens has not yet stabilized, recheck until stable.

Right Eye

The orientation mark on the right lens rotates left from the 6 o'clock position by 10° and remains stable in this position.

Compensation for this rotation should be done as follows:

Compensate the 10° axis drift by adding it to the manifest refraction axis.

Here is the Rx Prescribed:

O.D. -3.00D / -0.75D x 100°

Left Eye

The orientation mark on the left lens rotates right from the 6 o'clock position by 10° and remains stable in this position.

Compensate for the 10° axis drift by subtracting it from the manifest refraction axis.

Here is the Rx Prescribed:

O.S. -4.50D / -1.75D x 80°

If vision is acceptable, perform a slit lamp examination to assess adequate fit (centration and movement). If fit is acceptable, dispense the lenses instructing the patient to return in one week for reassessment (see dispensing and follow-up information in PATIENT MANAGEMENT).

All patients should be supplied with a copy of the PATIENT INSTRUCTION GUIDE for these lenses. Copies are available for download at www.acuvue.com.

MONOVISION FITTING GUIDELINES

A. Patient Selection

1. Monovision Needs Assessment

For a good prognosis, the patient should have adequately corrected distance and near visual acuity in each eye. The amblyopic patient or the patient with significant astigmatism (greater than 1.00D) in one eye may not be a good candidate for monovision correction with these lenses.

Occupational and environmental visual demands should be considered. If the patient requires critical vision (visual acuity and stereopsis), it should be determined by trial whether this patient can function adequately with monovision correction. Monovision contact lens wear may not be optimal for activities such as:

- visually demanding situations such as operating potentially dangerous machinery or performing other potentially hazardous activities; and
- driving automobiles (e.g., driving at night). Patients who cannot meet state driver's licensing requirements with monovision correction should be advised to not drive with this correction, OR may require that additional over-correction be prescribed.

2. Patient Education

All patients do not function equally well with monovision correction. Patients may not perform as well for certain tasks with this correction as they have with spectacles (multifocal, bifocal, trifocal, readers, progressives). Each patient should understand that monovision, as well as other presbyopic alternatives, can create a vision compromise that may reduce visual acuity and depth perception for distance and near tasks. Therefore, caution should be exercised when the patient is wearing the correction for the first time until they are familiar with the vision provided in visually challenging environments (e.g., reading a menu in a dim restaurant, driving at night in rainy/foggy conditions, etc.). During the fitting process, it is necessary for the patient to realize the disadvantages as well as the advantages of clear near vision and straight ahead and upward gaze that monovision contact lenses provide.

B. Eye Selection

1. Ocular Preference Determination Methods

Generally, the non-dominant eye is corrected for near vision. The following two methods for eye dominance can be used.

Method 1: Determine which eye is the "sighting eye." Have the patient point to an object at the far end of the room. Cover one eye. If the patient is still pointing directly at the object, the eye being used is the dominant (sighting) eye.

Method 2: Determine which eye will accept the added power with the least reduction in vision. Place a hand-held trial lens equal to the spectacle near ADD in front of one eye and then the other while the distance refractive error correction is in place for both eyes. Determine whether the patient functions best with the near ADD lens over the right or left eye.

2. Other Eye Selection Methods

Other methods include the "Refractive Error Method" and the "Visual Demands Method."

Refractive Error Method

For anisometropic correction, it is generally best to fit the more hyperopic (less myopic) eye for distance and the more myopic (less hyperopic) eye for near.

Visual Demands Method

Consider the patient's occupation during the eye selection process to determine the critical vision requirements. If a patient's gaze for near tasks is usually in one direction, correct the eye on that side for near.

Example: A secretary who places copy to the left side of the desk will function best with the near lens on the left eye.

C. Special Fitting Characteristics

1. Unilateral Vision Correction

There are circumstances where only one contact lens is required.

For example, an [REDACTED] would only require a near lens, whereas a bilateral [REDACTED] would require corrective lenses on

both eyes.

Examples:

A presbyopic emmetropic patient who requires a +1.75D ADD would have a +1.75D lens on the near eye and the other eye left without correction.

A presbyopic patient requiring a +1.50D ADD who is -2.50D myopic in the right eye and -1.50D myopic in the left eye may have the right eye corrected for distance and the left uncorrected for near.

2. Near ADD Determination

Always prescribe the lens power for the near eye that provides optimal near acuity at the midpoint of the patient's habitual reading distance. However, when more than one power provides optimal reading performance, prescribe the least plus (most minus) of the powers.

3. Trial Lens Fitting

A trial fitting is performed in the office to allow the patient to experience monovision correction. Lenses are fit according to the GENERAL FITTING GUIDELINES for base curve selection described in this Package Insert.

Case history and standard clinical evaluation procedure should be used to determine the prognosis. Determine the distance correction and the near correction. Next determine the near ADD. With trial lenses of the proper power in place, observe the reaction to this mode of correction.

Allow the lenses to settle for about 20 minutes with the correct power lenses in place. Walk across the room and have the patient look at you. Assess the patient's reaction to distance vision under these circumstances. Then have the patient look at familiar near objects such as a watch face or fingernails. Again assess the reaction. As the patient continues to look around the room at both near and distance objects, observe the reactions. Only after these vision tests are completed should the patient be asked to read print. Evaluate the patient's reaction to large print (e.g., typewritten copy) at first and then graduate to newsprint and finally smaller type sizes.

After the patient's performance under the above conditions is completed, tests of visual acuity and reading ability under

conditions of moderately dim illumination should be attempted.

An initial unfavorable response in the office, while indicative of a guarded prognosis, should not immediately rule out a more extensive trial under the usual conditions in which a patient functions.

4. Adaptation

Visually demanding situations should be avoided during the initial wearing period. A patient may at first experience some mild blurred vision, dizziness, headaches, and a feeling of slight imbalance. You should explain the adaptational symptoms to the patient. These symptoms may last for a brief minute or for several weeks. The longer these symptoms persist, the poorer the prognosis for successful adaptation.

To help in the adaptation process, the patient can be advised to first use the lenses in a comfortable familiar environment such as in the home.

Some patients feel that automobile driving performance may not be optimal during the adaptation process. This is particularly true when driving at night. Before driving a motor vehicle, it may be recommended that the patient be a passenger first to make sure that their vision is satisfactory for operating an automobile. During the first several weeks of wear (when adaptation is occurring), it may be advisable for the patient to only drive during optimal driving conditions. After adaptation and success with these activities, the patient should be able to drive under other conditions with caution.

D. Other Suggestions

The success of the monovision technique may be further improved by having the patient follow the suggestions below:

- Have a third contact lens (distance power) to use when critical distance viewing is needed.
- Have a third contact lens (near power) to use when critical near viewing is needed.
- Having supplemental spectacles to wear over the monovision contact lenses for specific visual tasks may improve the success of monovision correction. This is particularly applicable for those patients who cannot meet state driver's licensing requirements with monovision correction.
- Make use of proper [REDACTED] when carrying out visual tasks.

Monovision fitting success can be improved by the following suggestions:

- Reverse the distance and near eyes if a patient is having trouble adapting.
- Refine the lens powers if there is trouble with adaptation. Accurate lens power is critical for presbyopic patients.
- Emphasize the benefits of clear near vision and straight ahead and upward gaze with monovision.

The decision to fit a patient with monovision correction is most appropriately left to the Eye Care Professional in conjunction with the patient after carefully considering the patient's needs.

All patients should be supplied with a copy of the PATIENT INSTRUCTION GUIDE for these lenses. Copies are available for download at www.acuvue.com.

PATIENT MANAGEMENT

Dispensing Visit

Each sterile lens is supplied in a foil-sealed plastic package containing buffered saline solution with methyl ether cellulose. To remove the lens from the container, peel back the foil seal, place a finger on the lens, and slide the lens up the side of the bowl of the lens package until it is free of the container.

- Evaluate the physical fit and visual acuity of the lens on each eye.
- Teach the patient how to apply and remove his or her lenses.
- Explain daily disposable lens wear and schedule a follow-up examination.
- **Provide the patient with a copy of the PATIENT INSTRUCTION GUIDE for these lenses. Copies are available for download at www.acuvue.com.**

REVIEW THESE INSTRUCTIONS WITH THE PATIENT SO THAT HE OR SHE CLEARLY UNDERSTANDS THE PRESCRIBED WEARING AND REPLACEMENT SCHEDULES.

Follow-Up Examinations

Follow-up care (necessary to ensure continued successful contact lens wear) should include routine periodic progress examinations, management of specific problems, if any, and CR-6450 v4.0 JVC CONFIDENTIAL pp. 1 the patient of the wear schedule, daily disposable modality, and proper lens handling procedures.

Recommended Follow-up Examination Schedule (complications and specific problems should be managed on an individual patient basis):

1. One week from the initial lens dispensing to patient
2. One month post-dispensing
3. Every three to six months thereafter

NOTE: Preferably, at the follow-up visits, lenses should be worn for at least six hours.

Recommended Procedures for Follow-up Visits:

1. Solicit and record patient's symptoms, if any.
2. Measure visual acuity monocularly and binocularly at distance and near with the contact lenses.
3. Perform an over-refraction at distance and near to check for residual refractive error.
4. With the biomicroscope, judge the lens fitting characteristics (as described in the **GENERAL FITTING GUIDELINES**) and evaluate the lens surface for deposits and damage.
5. Following lens removal, examine the cornea and conjunctiva with the biomicroscope and fluorescein (unless contraindicated).
 - The presence of vertical corneal striae in the posterior central cornea and/or corneal neovascularization is indicative of excessive corneal edema.
 - The presence of corneal staining and/or limbal-conjunctival hyperemia can be indicative of an unclean lens, a reaction to solution preservatives, excessive lens wear and/or a poorly fitting lens.
 - Papillary conjunctival changes may be indicative of an unclean and/or damaged lens.
6. Periodically perform keratometry and spectacle refractions. The values should be recorded and compared to the baseline measurements.

4R-6469N4IDENTIAL

If any observations are abnormal, use professional judgment to alleviate the problem and restore the eye to optimal conditions. If

the criteria for successful fit are not satisfied during any follow-up examinations, repeat the patient's trial fitting procedure and refit the patient.

WEARING SCHEDULE

The wearing schedule should be determined by the Eye Care Professional. Regular checkups, as determined by the Eye Care Professional, are also extremely important.

Patients tend to overwear the lenses initially. The Eye Care Professional should emphasize the importance of adhering to the initial maximum wearing schedule. Maximum wearing time should be determined by the Eye Care Professional based upon the patient's physiological eye condition, because individual response to contact lenses varies.

The maximum suggested wearing time for these lenses is:

Day	Hours
1	6-8
2	8-10
3	10-12
4	12-14
5 and after	all waking hours

REPLACEMENT SCHEDULE

These lenses are indicated for daily disposable wear and should be discarded upon removal.

LENS CARE DIRECTIONS

When lenses are prescribed for daily disposable wear, the Eye Care Professional should provide the patient with appropriate and adequate warnings and instructions for daily disposable lens wear at the time they are dispensed.

CR-6459, v4.0

The Eye Care Professional should review with patients that no cleaning or disinfection is needed with daily disposable lenses. Patients should always dispose of lenses when they are removed and have spare lenses or spectacles available.

Basic Instructions

- Always wash, rinse, and dry hands before handling contact lenses.
- Do not use saliva or anything other than the recommended solutions for lubricating or rewetting lenses. Do not put lenses in the mouth.
- Eye Care Professionals may recommend a lubricating/rewetting solution which can be used to wet (lubricate) lenses while they are being worn to make them more comfortable.

Care for a Sticking (Non-Moving) Lens

If the lens sticks (stops moving), the patient should be instructed to apply a few drops of the recommended lubricating or rewetting solution directly to the eye and wait until the lens begins to move freely on the eye before removing it. If non-movement of the lens continues after a few minutes, the patient should immediately consult the Eye Care Professional.

EMERGENCIES

The patient should be informed that if chemicals of any kind (household products, gardening solutions, laboratory chemicals, etc.) are splashed into the eyes, the patient should: FLUSH EYES IMMEDIATELY WITH TAP WATER AND IMMEDIATELY CONTACT THE EYE CARE PROFESSIONAL OR VISIT A HOSPITAL EMERGENCY ROOM WITHOUT DELAY.

HOW SUPPLIED

Each UV-blocking sterile lens is supplied in a foil-sealed plastic package containing buffered saline solution with methyl ether cellulose. The plastic package is marked with the following:

- ACUVUE OASYS® 1-Day: base curve, power, diameter, lot number, and expiration date
- ACUVUE OASYS® 1-Day CR-6459, v4.0 MATISM: base curve, power, diameter, cylinder, axis, lot Page 136 of 200 and expiration date

JVC CONFIDENTIAL

REPORTING OF ADVERSE REACTIONS

All serious adverse experiences and adverse reactions observed in patients wearing these lenses or experienced with these lenses should be reported to:

Johnson & Johnson Vision Care, Inc.
[name]
[name]
USA
[contact]
www.acuvue.com

Johnson & Johnson Vision Care, Inc.
[name]
[name]
USA
[contact]
www.acuvue.com

20401080

©Johnson & Johnson Vision Care Companies 2016
In Canada: Johnson & Johnson Vision Care, division of Johnson & Johnson, Inc.
In USA: Johnson & Johnson Vision Care, Inc.
Printed in USA.
Revision date: 09/16
Revision number: AO-03-16-13

ACUVUE® OASYS® and [REDACTED] e™ are trademarks of
the Johnson & Johnson Vision Care Companies

Clinical Study Protocol
Johnson & Johnson Vision Care, Inc.

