2.11	General lens fit assessment	
The fitting characteristics of the lens in both eyes will be assessed using a slit lamp. Lens position (centration, limbal exposure, edge lift) and movement (primary and up gaze as well as push-up) will be assessed. Fit acceptability is defined as any lens that does not display the following general fit characteristics:
 
 • Limbal exposure (presence of clear cornea) in any direction of gaze. • Edge lift • Insufficient movement in all three movement assessments (primary gaze, up-gaze and push-up test). • Excessive movement in primary gaze 
If the general fit is unacceptable for either eye, the subject will be discontinued (proceed to exit evaluation).

Clinical Study Protocol
Johnson & Johnson Vision Care, Inc.

Visit 2: Lens Fitting #1		
Step	Procedure	Details
2.12	Spherical over-refraction	
Perform monocular spherical over-refraction. Where possible, use the duo-chrome test to refine the endpoint as described in step 1.11 (the final spherical endpoint may be determined binocularly).
 
The spherical over-refraction must be plano in both eyes to continue.
 
If a non-plano over-refraction is found in either eye, the lens(es) must be refit with the indicated change in sphere power. If the indicated lens power is not available for either eye (e.g., outside the available SKU range), the subject will be discontinued (proceed to final evaluation).

2.13	Lens modification (if necessary)	
If modification is necessary in one or both eyes, select the reason for refitting lenses:
 
 • (For toric lenses only) The settled lens rotation is such that a different cylinder axis would be more appropriate (use the LARS rule to determine the replacement lens cylinder axis) • The spherical over-refraction is not plano • Other (specify reason) 
Repeat steps 2.8 through 2.12 for one or both eyes, as appropriate.
 
A maximum of 2 lens modifications are allowed per eye. If, for either eye, the fit is not successful after 2 modifications, the subject will be discontinued (proceed to final evaluation).

2.14	Stop timer for timing contact lens fit	Once a successful lens fit is achieved (no further modifications necessary and plano over-refraction in both eyes), record the stopping time for completing the contact lens fitting procedures.

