2.15	Post-fit PRO questionnaire	Subjects will complete a CLUE questionnaire regarding the initial comfort, vision and handling of the study lenses.

Clinical Study Protocol
Johnson & Johnson Vision Care, Inc.

Visit 2: Lens Fitting #1		
Step	Procedure	Details
2.16	Exit visual acuity	Record the exit monocular distance Snellen visual acuity for each eye with the subject wearing the study lenses.
2.17	Dispensing criteria	
Lenses may be dispensed if both following conditions are met:
 
 1. The monocular distance visual acuity with the study lenses is equal to or better than 20/40 in each eye. 2. The subject indicates that the comfort and vision with the study lenses is acceptable. If either of these conditions is not met, the subject will be discontinued (proceed to exit evaluation).
2.18	Dispensing instructions	
If the study lenses are suitable for dispensing:
 
 • Instruct the subject to wear the study lenses for at least 8 hours per day (in a daily wear / daily disposable modality) on at least 5 days of the wear period. 
Subjects must not wear their habitual contact lenses at any time during the dispensing period.
 
 • Provide the subject with a copy of the Patient Instruction Guide. • Preservative-free rewetting drops are permitted, if needed. • Dispense enough lenses for the subject to complete the wear period (i.e., up to and including their scheduled follow-up visit). At the investigator's discretion, in instances where there is a high likelihood of the subject needing replacement lenses (e.g., due to subject activities, unavailability of subject or site during the wear period, high likelihood of lens tears, etc.), one additional spare pair may be dispensed. 
Note: In the event that a subject requires additional lenses due to loss or damage, they may return to the clinical site for lens replacement. As much as reasonably possible, damaged lenses and packaging should be

Clinical Study Protocol
Johnson & Johnson Vision Care, Inc.

Visit 2: Lens Fitting #1		
Step	Procedure	Details

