4.6	Distance ETDRS visual acuity	
Measure monocular distance high-luminance, high-contrast (HLHC) and high-luminance, low-contrast (HLLC) visual acuity using ETDRS charts at 4 meters with the subject wearing the habitual spectacle correction.
 
Measure each eye using the charts shown in the table below:
 
  
 Condition	HLHC	HLLC	
   
 Room illumination	> 400 lux	
 
 Chart luminance	120 - 200 cd/m²	
 
 Eye	OD	OS	OD	OS	
 
 Charts	HC-1	HC-2	LC-1	LC-2	
  
 
Recorded letter-by-letter results into EDC.
			Condition	HLHC	HLLC	Room illumination	> 400 lux		Chart luminance	120 - 200 cd/m ²		Eye	OD	OS	OD	OS	Charts	HC-1	HC-2	LC-1	LC-2
Condition	HLHC	HLLC																					
Room illumination	> 400 lux																						
Chart luminance	120 - 200 cd/m ²																						
Eye	OD	OS	OD	OS																			
Charts	HC-1	HC-2	LC-1	LC-2																			
4.7	Biomicroscopy	
The FDA Slit Lamp Classification Scale will be used to grade findings. If any slit lamp finding is graded as 3 or worse, the subject must be discontinued, an adverse event will be recorded, and the subject will be monitored as per the guidelines given in section 13.
 
Should the clearance of the fluorescein need to be expedited, preservative free rewetting drops or artificial tears may be instilled.
																					
4.8	Continuance	Verify that the subject is eligible to continue in the study.																					

Visit 4: Lens Fitting #2

The steps followed will be the same as those listed under Visit 2: Lens fitting #1.

Clinical Study Protocol

Johnson & Johnson Vision Care, Inc.

VISIT 5

Visit 5 will occur 5 to 9 days following Visit 4. Subjects must present to this visit wearing the study lenses in both eyes, and lenses must have been worn for at least 1 hour prior to the visit.

Subjects should bring their own habitual spectacles or contact lenses to this visit to wear following study lens removal.

Visit 5: Follow-up #2		
Step	Procedure	Details

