8.2. Withdrawal/Discontinuation from the Study

A subject will be withdrawn from the study for any of the following reasons:

- Subject withdrawal of consent.
- Subject not compliant to protocol.
- Subject lost to follow-up.
- Subject no longer meets eligibility criteria (e.g. the subject becomes pregnant).
- Subject develops significant or serious adverse events necessitating discontinuation of study lens wear.
- Subjects who have experienced a Corneal Infiltrative Event (CIE).
- Investigator's clinical judgment regarding the subject safety reasons (that it is in the best interest of the subject to stop treatment).
- Subject misses any study visits.
- Subject not compliant with study lens wear schedule.
- Subject not successfully dispensed due to lack of efficacy and safety including poor vision, poor comfort or unacceptable fit.

For discontinued subjects, the Investigator will:

- Complete the current visit (scheduled or unscheduled).
- Complete the Final Evaluation, indicating the reason that the subject was discontinued from the study.
- Record the spherocylindrical refraction with best corrected distance visual acuity.
- Collect used test article(s) (worn or brought to the visit) from the subject and discard them, unless otherwise stated in section 7.2.
- Collect all unused test article(s) from the subject.
- Make arrangements for subject care, if needed, due to their study participation

Additional subjects may be enrolled if a subject discontinues from the study prematurely.

In cases where a subject is lost to follow-up, every possible effort must be made to contact the subject and determine the reason for discontinuation/withdrawal. The measures taken to follow up must be documented including two written attempts and a certified letter (or equivalent) as the final attempt.

Clinical Study Protocol

Johnson & Johnson Vision Care, Inc.

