A properly fit lens will center and completely cover the cornea (i.e., no limbal exposure), have sufficient movement to provide tear exchange under the contact lens with the blink, and be comfortable. The lens should move freely when manipulated digitally with the lower lid, and then return to its properly centered position when released.

2. Criteria of a Flat Fitting Lens

A flat fitting lens may exhibit one or more of the following characteristics: decentration, incomplete corneal coverage (i.e., limbal exposure), excessive movement with the blink, and/or edge standoff. If the lens is judged to be flat fitting, it should not be dispensed to the patient.

3. Criteria of a Steep Fitting Lens

A steep fitting lens may exhibit one or more of the following characteristics: insufficient movement with the blink, conjunctival indentation, and resistance when pushing the lens up digitally with the lower lid. If the lens is judged to be steep fitting, it should not be dispensed to the patient.

If the initial trial base curve is judged to be flat or steep fitting, the alternate base curve, if available, should be trial fit and evaluated after the patient has adjusted to the lens. The lens should move freely when manipulated digitally with the lower lid, and then return to a properly centered position when released. If resistance is encountered when pushing the lens up, the lens is fitting tightly and should not be dispensed to the patient.

E. Final Lens Power (Spherical)

A spherical over-refraction should be performed to determine the final lens power after the lens fit is judged acceptable. The spherical over-refraction should be combined with the trial lens power to determine the final lens prescription. The patient should [REDACTED] good visual acuity with the correct lens power unless there is excessive residual astigmatism.

Example 1	
Diagnostic lens:	-2.00D
Spherical over-refraction:	-0.25D
Final lens power:	-2.25D

Example 2	
Diagnostic lens:	-2.00D
Spherical over-refraction:	+0.25D
Final lens power:	-1.75D

If vision is acceptable, perform a slit lamp examination to assess adequate fit (centration and movement). If the fit is acceptable, dispense the lenses and instruct the patient to return in one week for reassessment (see dispensing and follow up information in **PATIENT MANAGEMENT**).

All patients should be supplied with a copy of the PATIENT INSTRUCTION GUIDE for these lenses. Copies are available for download at www.acuvue.com.

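### Step 2.11 accepts a lens with insufficient push-up movement if it moves adequately in primary gaze or up-gaze, an unexplained departure from the appended package insert (minor, cheap to fix)

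*Combined protocol and SAP*

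**What the plan says.** Protocol section 7.2, Visit 2, step 2.11 has the investigator assess lens position and movement at the slit lamp, with movement judged in primary gaze, in up-gaze and on push-up. The definition works by exclusion: "Fit acceptability is defined as any lens that does not display the following general fit characteristics". Four faults follow: limbal exposure, edge lift, excessive movement in primary gaze, and "Insufficient movement in all three movement assessments (primary gaze, up-gaze and push-up test"). The last is the only one that concerns a tight lens. The consequence is stated: "If the general fit is unacceptable for either eye, the subject will be discontinued (proceed to exit evaluation").

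Step 2.17 then sets the dispensing criteria: "Lenses may be dispensed if both following conditions are met". The two conditions are acuity of 20/40 or better in each eye, and the subject finding comfort and vision acceptable. Neither concerns movement. For the second fitting, at Visit 4, "The steps followed will be the same as those listed under Visit 2: Lens fitting #1". Section 8.2 lists among its reasons for withdrawal "Subject not successfully dispensed due to lack of efficacy and safety including poor vision, poor comfort or unacceptable fit", without a separate definition of unacceptable fit.

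Appendix C reproduces the package insert covering both study lenses. Under General Fitting Guidelines, part D, the criteria for a properly fit lens include "The lens should move freely when manipulated digitally with the lower lid, and then return to its properly centered position when released". The criteria for a steep lens name resistance to digital push-up as one possible sign and say that a lens judged steep should not be dispensed. The part closes with "If resistance is encountered when pushing the lens up, the lens is fitting tightly and should not be dispensed to the patient". The toric guidelines say that most of the fitting procedure is the same for toric lenses.

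**The concern.** The two texts treat push-up differently. In the insert, resistance on push-up is by itself a reason to withhold the lens. In step 2.11, insufficient push-up movement counts only when both gaze assessments are insufficient as well. The protocol gives no reason for the more permissive rule.

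Section 8.2 treats unacceptable fit as an efficacy and safety ground for not dispensing, so the definition in step 2.11 helps decide who goes home in a study lens. A subject could be sent home in a fit that the lens's own labelling says to withhold, and the next scheduled fit assessment is 5 to 9 days later. What is at stake is a small point of subject protection, not the statistical conclusions.

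**Working it through.** **Comparing the two rules.** Grade each of the three movement assessments as sufficient (S) or insufficient (I), and assume no other fit fault. There are 2 × 2 × 2 = 8 patterns, and push-up is insufficient in 4 of them:

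| Primary gaze | Up-gaze | Push-up | Step 2.11 | Insert, reading insufficient push-up movement as resistance |
|---|---|---|---|---|
| I | I | I | Reject | Do not dispense |
| S | I | I | Accept | Do not dispense |
| I | S | I | Accept | Do not dispense |
| S | S | I | Accept | Do not dispense |

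Step 2.11 rejects 1 of these 4, so the rules disagree on 4 − 1 = 3. The other four patterns have sufficient push-up movement and do not bear on this point.

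**Looking for a later check.** Step 2.17 has no movement condition. Visit 4 inherits the Visit 2 steps. Section 8.2 refers to unacceptable fit without redefining it. The assessments at steps 3.9 and 5.10 repeat the same definition, but at follow-up, after the lenses have been worn, and with no stated action. No written rule after step 2.11 catches the three accepted patterns.

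**Cost of a stricter rule in power.** Subjects who fail the fit are discontinued, so the question is how many completers can be lost. Inputs from section 14.2, Table 8: difference −0.025 logMAR, SD 0.09, 153 completers, two-sided type I error 0.05, paired t test.

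SD of the paired difference = 0.09 × √(2(1 − ICC)); noncentrality = 0.025 × √n ÷ (SD of difference); n − 1 degrees of freedom.

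| ICC | SD of difference | Power at n = 153 (matches Table 8) | Smallest n with power ≥ 0.80 | Power one subject lower | Completers that can be lost |
|---|---|---|---|---|---|
| 0.3 | 0.09 × √1.4 = 0.1065 | 0.823 | 145 (0.802) | 0.799 | 153 − 145 = 8 |
| 0.4 | 0.09 × √1.2 = 0.0986 | 0.876 | 124 (0.800) | 0.797 | 153 − 124 = 29 |
| 0.5 | 0.09 × √1.0 = 0.0900 | 0.927 | 104 (0.801) | 0.797 | 153 − 104 = 49 |

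The historical intraclass correlation in Table 7 is 0.399, close to the middle row. These figures measure only the cost of the change; they are not evidence of the gap.

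**The case against.** - **The grading procedure cannot be seen.** Step 2.11 speaks of insufficient movement, the insert of resistance. The Lens Fitting Characteristics procedure in Appendix D, where grading would be expected, is redacted, and redacted text is not missing from the plan. If it separates the two ideas, the overlap with the insert's do-not-dispense sentence could be smaller than the table shows. This stands as a limit. It does not remove the point, because a lens graded insufficient on push-up can hardly also move freely when manipulated with the lower lid, which is what the insert expects of a properly fit lens.
- **The insert is not a study rule.** This is correct. Sections 1.4 and 1.5 cite it for risk and benefit information and for prior clinical data. The protocol departs from it elsewhere, for example on vertex correction and on hours of wear before follow-up. A reader might therefore infer a protocol breach, and the documents do not support that. Those other departures, however, do not concern advice to withhold a lens.
- **The quoted sentence closes a paragraph about trying another base curve, and steepness is a matter of judgement.** The general criteria just above it say the same about push-up, so the context does not change its meaning. The insert does also expect sufficient movement with the blink, and a push-up rule alone would not bring the protocol fully into line with it. That is fair: the alignment is partial.
- **Other safeguards exist.** Section 4.2 specifies experienced optometrists, lenses are discarded daily, comfort must be acceptable before dispensing, and section 8.2 lets the investigator stop on safety grounds. These limit exposure, but none is a push-up rule.
- **No consequence is shown.** A reader might take three patterns out of four as a rate, or infer bias in the lens comparison. Neither follows. The patterns are not equally likely, and the same rule applies to both lenses.

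**Conclusion.** The point holds as a minor, inexpensive safety improvement. Under step 2.11 a lens with insufficient push-up movement is acceptable, and can be dispensed at Visits 2 and 4, whenever movement is adequate in primary gaze or up-gaze. This departs without explanation from the labelling appended for both lenses.

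The count of three disputed patterns assumes that a lens graded insufficient on push-up is one the insert would regard as resisting push-up. That is the natural reading, but it cannot be confirmed while the grading procedure is redacted. How often such lenses occur is unknown, and no figure is assumed. No protocol rule is broken, no specific harm is shown, and no effect on the primary hypothesis or the first secondary hypothesis is claimed. Confidence is medium.

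**What to change.** In step 2.11, replace the third bullet with: *Insufficient movement on the push-up test, whatever the movement in primary gaze or up-gaze*, graded by the existing Lens Fitting Characteristics procedure. The bullet should not use resistance as a synonym, since the redacted scale may define its terms differently. The pattern that is rejected now stays rejected, because it includes push-up, and Visit 4 inherits the change. The same wording could go into steps 3.9 and 5.10 for consistency, where it alters no action. Blink movement stays with the investigator. If the sponsor prefers the all-three rule, one sentence giving the reason would remove the unexplained conflict.

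The cost is one bullet and no new assessment, plus a small, unquantified number of extra discontinuations at fitting. The insert's other remedy, an alternate base curve, is not available: Table 1 supplies only 8.5 mm. The insert lists 9.0 mm for the spherical lens but not for the toric, so adding it would let the two lenses differ in base curve, and it is not proposed. Section 4.3 allows replacement of discontinued subjects at the sponsor's discretion. Without replacement, the tightest case in Table 8 at a difference of -0.025 (ICC 0.3) tolerates 8 lost completers before power falls below 80%.
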